8.6 Ventilatory Ration (VR)

Ventilatory ratio (VR) is a simple bedside measurement of ventilation, which is calculated using the below formula (20):

$$VR = \frac{\dot{V}_{E_{\text{measured}}} \times Pa_{CO_2\text{measured}}}{\dot{V}_{E_{\text{predicted}}} \times Pa_{CO_2\text{predicted}}}$$

$\dot{V}_{E_{\text{predicted}}}$ is taken to be 100 (ml kg⁻¹ min⁻¹) based on predicted body weight, and $Pa_{CO_2\text{predicted}}$ is taken to be 5 kPa.

8.7 Ordinal Scale for Clinical Improvement (OSCI)

Ordinal Scale for Clinical Improvement (OSCI) is a 9-point scale, where 0 corresponds to no infection and 8 corresponds death. OSCI will be used to evaluate clinical outcomes at days 0, 7, 14, 28 for all patients, either by chart review or by telephone interviews after hospital discharge.

[figure not shown]
Table 4. WHO Ordinal Scale for Clinical Improvement

Patient State	Descriptor	Score
Uninfected	No clinical or virological evidence of infection	0
Ambulatory	No limitation of activities	1
	Limitation of activities	2
Hospitalized Mild Disease	Hospitalized, no oxygen therapy	3

	Oxygen by mask or nasal prongs	4
Hospitalized Severe Disease	Non-invasive ventilation or high-flow oxygen	5
	Intubation and mechanical ventilation	6
	Ventilation + additional organ support – pressors, RRT, ECMO	7
	Death	8

8.8 Radiographic Assessment of Lung Edema (RALE) score

Radiographic Assessment of Lung Edema (RALE) score will be used to evaluate the extent and density of alveolar opacities on chest radiographs at day 1, 2, 3 and 7. To determine the RALE score, each radiograph was divided into quadrants, defined vertically by the vertebral column and horizontally by the first branch of the left main bronchus. Each quadrant was assigned a consolidation score from 0 to 4 to quantify the extent of alveolar opacities, based on the percentage of the quadrant with opacification and a density score from 1 to 3 to quantify the overall density of alveolar opacities, unless the consolidation score for that quadrant was 0. The density score (1=hazy, 2=moderate, 3=dense) allows for more quantitative assessment of the density of opacification by quadrant. To calculate the final RALE score, the product of the consolidation and density score for each quadrant were summed for a final RALE score ranging from 0 (no infiltrates) to 48 (dense consolidation in >75% of each quadrant). (21) Details of the RALE score are provided in Figure 1.

^aConsolidation is scored for each quadrant

^bDensity is scored for each quadrant that has a consolidation score ≥ 1

^cIf Quadrant consolidation score is – then Quadrant score is 0

Figure 1. Consolidation and density scoring in the Radiographic Assessment of Lung Oedema (RALE) score (panel A). Calculation of the RALE score (panel B). (21)

8.9 Ventilator Free Days

Ventilator Free Days (VFDs) to day 28 are defined as the number of days from the time of initiating unassisted breathing to day 28 after study product administration, assuming survival for at least

two consecutive calendar days after initiating unassisted breathing and continued unassisted breathing to day 28. If a patient returns to assisted breathing and subsequently achieves unassisted breathing to day 28, VFDs will be counted from the end of the last period of assisted breathing to day 28. A period of assisted breathing lasting less than 24 hours and for the purpose of a surgical procedure will not count against the calculation of VFDs. If a patient was receiving assisted breathing at day 27 or dies prior to day 28, VFDs will be zero. Patients transferred to another hospital or other health care facility will be followed to day 28 to assess this endpoint. Similarly, we will use the same methodology to calculate ventilator free days over 7 and 14 days.

9 HANDLING OF MISSING VALUES AND OTHER DATA CONVENTIONS

Subjects will be allocated a 5-digit subject number and their inclusion/exclusion criteria eligibility will be determined prior to randomization. Subjects who do not satisfy all inclusion/exclusion criteria will be excluded from the study without randomization. Subjects who are not randomized are considered screening failures and a screening log will be required to record some de-identified data (see Clinical Protocol – Appendix C).

Prior to initiation of study product administration, subjects must achieve stable baseline for at least two hours and still be eligible for the trial, meeting the following key criteria and the timeline:

- Eligibility for the trial - ARDS develops less than 72 hours since first meeting ARDS criteria per the Berlin definition of ARDS
- Eligibility for the trial - Must begin to administer study product within 14 days of initial ICU admission
- Eligibility - The $\text{PaO}_2/\text{FiO}_2$ remains less than 250 mmHg after consent obtained and before study product is administered

For patients who have been randomized but who do not initiate study product administration, we will complete the following instruments: Screening Log, Infusion Eligibility Assessment and Pre-Infusion Baseline Assessment.

If a patient or surrogate withdraws consent for the study, we will discuss with the subject or surrogate the importance of complete data follow-up for the purposes of our safety analyses and determine if they are at least willing to participate in a follow up telephone call to ascertain survival. All patients who initiate study product administration will be analyzed for efficacy and safety endpoints, as well as incorporated with the relevant mixed model analyses, regardless of whether they complete or discontinue the study (e.g., consent withdrawn, infusion discontinuation, et al.).

We will make every effort to fulfill all the requirements of the protocol concerning the collection and management of data. Missing data will be summarized according to the number of subjects, the time-points where the data are missing and reasons of missing. No imputation will be applied

for missing data, unless indicated in the Statistical Analysis Plan and future amendments, if applicable.

The Data Manager at CCC will examine outliers and extreme values in a blinded manner prior to data locking. If any outlier appears to be influential and has been validated as is, sensitivity analyses may be performed by doing one analysis with the actual values and at least one other analysis eliminating or reducing the outlier effect, and differences between these two results will be discussed.

10 SAMPLE SIZE DETERMINATION

The sample size for this trial will be 60 patients in the hMSCs arm and 60 patients in the placebo arm, for a total of 120 patients with a balanced randomization of patients with $\text{PaO}_2:\text{FiO}_2 < 150$ mmHg. This sample size was determined on the basis of feasibility.

Given the sample size of 60 per treatment condition, in this multisite, randomized trial using oxygenation index as the primary outcome and measures taken at 6 time points, it is estimated the study will have 80% power to detect a difference between conditions for an effect size as low as 0.43. Using the pilot data from Day 4, for example, this would translate to approximately a difference of 1.29 in the oxygenation index.

11 ANALYSIS SETS/POPULATIONS

A total of three populations will be used for all summaries and analyses. Subjects who have satisfied the population criteria will be classified in the designated population and will only be included in analyses for which they have available data.

Intent-to-Treat (ITT) Population

The analysis of the primary and secondary outcome will be based on the intention-to-treat (ITT) principle.

In this study, critical ill patients with ARDS often experience minute-to-minute changes in vital signs. Therefore, it is not uncommon that the patients will not achieve a stable baseline for 2 hours and initiate the infusion of study product within 14 days of initial ICU admission, or their $\text{PaO}_2:\text{FiO}_2$ ratio will improve to over 250 mmHg and they no longer qualify. In these cases, patients will be excluded and will not count toward the target enrollment of 120. Therefore, in this Phase 2b trial, the ITT population will be modified and include all subjects who are randomized, achieve baseline stability and initiate the study product administration, regardless of their compliance with the trial protocol or lack of study completion if allocated to the intervention group.

Since the study treatment is a single infusion of study product, a subject is unlikely to be withdrawn by investigators due to safety concerns because there is only a single treatment to be administered.

However, a surrogate or subject may withdraw consent for study participation either before, during or after study product administration. For subjects who are withdrawn prior to the initiation of study product infusion, they will not be included in ITT population. For subjects who are withdrawn during or after study product administration, they will be included in ITT population. The ITT population will be used to present primary efficacy endpoint and secondary efficacy endpoints by allocated randomization. Subjects will be summarized according to the treatment to which they were randomized, regardless of which treatment they actually received.

Per Protocol Population

It is possible that there will be a number of deviations from the trial protocol. In this statistical plan, protocol deviations are considered to either non-compliance with the allocated intervention or non-adherence to other elements of the protocol, for example, non-adherence with inclusion or exclusion criteria, subsequent withdrawal during study product administration, outcome assessments completed outside the pre-specified windows, or other deviation from the protocol.

In this study, the Per Protocol (PP) population is defined as all patients who will complete the study without major protocol deviations. The PP population will be fixed following clinical review of all protocol deviations at the end of the study and prior to unblinding and data locking. Due to the blinding feature of the study, the analyses of endpoints using PP population will not be feasible in the interim report to DSMB. However, as a sensitivity analysis, the analysis of efficacy and safety endpoints using PP population will be included in the final study report.

Safety Population

The Safety population will be used for the analysis of safety, including adverse events, toxicity and safety laboratory evaluation. In this study, the Safety population is defined as all randomized who started the study product administration, regardless of infusion completion.

Due to the blinding feature of the trial, the safety and adverse events will be summarized using ITT population in the interim report for 60 patients to the DSMB. However, in the final report, the safety summaries and adverse events listings will be grouped by actual treatment received.

12 STATISTICAL METHODOLOGY

12.1 Disposition of Subjects

Modified Intent-to-treat (ITT) population will be summarized using frequencies and percentages from the screened populations, by recruitment site and as total. Patients who have been randomized but not receive study product administration and the related reasons will also be listed.

Frequency and percentage of MITT populations with follow-up up to 28 days for adverse events, up to 60 days for vital status, and up to six months for long-term follow-up, as well as patients with early withdrawal from the study, and the related reasons.

12.2 Randomization, Stratification and Allocation Concealment

After obtaining informed consent from the subject or the subject's legal authorized representative (LAR), the study investigators or coordinators will inform the staff at Bone Marrow Transplant (BMT) Lab by a written document. BMT staffs will use a unique Personal Identification Number (PIN) to access the Clinical Coordinating Center web-based randomization system to input participant details. The randomization will use a computer-generated permuted block design with a 1:1 ratio, and stratified by $\text{PaO}_2:\text{FiO}_2 < 150$ mmHg and the presence or absence of trauma. If a randomized patient does not initiate the study product administration (e.g. study withdrawal, failure to achieve stable baseline, etc), the randomization will be returned to the pools.

12.3 Blinding

The study is designed as double-blinded. BMT laboratory staff will conduct randomization and prepare the study product. The BMT team will not share the randomization assignment to the participants and their families, as well as the research team (Site Investigators, Study Coordinators, Data Manager and Statistician). The data analysis conducted by the Statistician for the interim DSMB report after 60 patients, as well as the primary analysis of the main results will be undertaken in a blinded manner. The study treatment will be coded as "A" and "B".

12.4 Protocol Deviation

Protocol deviations should be recorded by the Site Investigators and Study Coordinators and will be reported to the CCC at UCSF. Any protocol deviations will be listed by individual subject and include a description of the deviation, the date/time of the deviation (if available), study day of the deviation, time point (if applicable). The number and proportions of subjects categorized as non-compliers will be summarized for each treatment separately. Protocol deviations will be also summarized by sites. Protocol deviations will be based on MITT population.

All protocol deviations will be discussed between Investigators, Data Manager, Biostatistician, and Study Coordinators, and report to the DSMB before database lock.

12.5 General Methodology

Study Investigators, Study Coordinators, Data Manager and Statistician will be blinded to treatment assignment (randomization assignment will be coded as A group vs. B group) during the study prior to data lock.

Parameters ascribed to the safety and efficacy of patients will be summarized by modified ITT population defined in Section 11.

Continuous variables will be summarized using tables of descriptive statistics: number of patients with recorded observations, mean, standard deviation, median, minimum, maximum and interquartile range (IQR). Comparison of continuous parameters between two groups will be performed using T-test or Wilcoxon-Mann-Whitney test, as appropriate. Categorical variables will be summarized using counts and percentages, and compared between two groups using Pearson's chi-square or Fisher exact test, as appropriate. Based on the data shown in our previous Phase 2a

study, biomarker data will be summarized with descriptive statistics described above on original scale and log-transformed scale.

All statistical tests will be two-sided and will be performed at the 5% level of significance, unless otherwise stated. P-values will be rounded to three decimal places. P-values less than 0.001 will be reported as < 0.001 in tables. In bivariate analyses, P-values will not be adjusted for the comparisons of repeated outcomes between treatment allocations at multiple timepoints. Additional ad-hoc analyses may be conducted as deemed suitable.

As there is a single primary endpoint, and the secondary endpoints are to be used only in providing additional supportive exploratory information, there will be no adjustment for multiple testing.

All outputs will be produced using SAS and STATA (most up to date version available).

12.6 Analysis for Primary Efficacy Endpoint

The primary endpoint is the changes in the oxygenation index from the baseline to the time-points at 6, 12, 18, 24, 30 and 36 hours after infusion of study product. The oxygenation index will only be calculated when the patient is still being ventilated with positive pressure. If patient is on pressure support, oxygenation index will be treated as missing because the mean airway pressure is not reliable.

Descriptive summary statistics (e.g. means and standard deviations, or median with inter-quartile, as appropriate) will be presented for the oxygenation index values, as well as the changes of oxygenation index from the baseline to each following timepoint by allocated group in modified ITT population.

The change of oxygenation index, by allocated treatment groups in modified ITT Population, will be compared using two linear mixed-effects regression models: unadjusted and adjusted model. Both models will be estimated using maximum likelihood estimation, which will allow the inclusion of all collected data, regardless of the number of assessments available for assessment. All models will include the stratification variables: $\text{PaO}_2/\text{FiO}_2$ ($< 150 \text{ mmHg}$ or $\geq 150 \text{ mmHg}$) and trauma status (trauma vs. non-trauma). Terms in the unadjusted linear mixed-effects regression model will include the two stratification variables, treatment condition (active or placebo), time of assessment (by hour), condition-by-time, recruitment site and a site-by-treatment interaction term. A test of the treatment condition will directly test the main research question. The adjusted linear mixed-effects regression model will include all the variables from the unadjusted model described above plus covariates identified by preliminary analysis as potentially confounding due to baseline differences ($p\text{-value} < 0.20$). The treatment effects may vary with ARDS severity ($\text{PaO}_2/\text{FiO}_2$) or by trauma status, thus the interaction terms will be also included. Both unadjusted and adjusted models will be presented with coefficient with 95% confidence intervals.

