7.3 Exclusion Criteria

1. Age less than 18 years
2. Greater than 72 hours since first meeting ARDS criteria per the Berlin definition of ARDS
3. Greater than 14 days since initial ICU admission
4. Inability to administer study product within 14 days of initial ICU admission
5. $\text{PaO}_2/\text{FiO}_2 \geq 250$ mmHg after consent obtained and before study product is administered
6. Unable to obtain informed consent/no surrogate available
7. Pregnant or lactating
8. In custody of law enforcement officials
9. Burns $>$ 20% of total body surface area
10. WHO Class III or IV pulmonary hypertension
11. History of cancer treatment in the last 2 years except for non-melanotic skin cancers
12. Underlying medical condition for which 6-month mortality is estimated to be $>$ 50%
13. Moribund patient not expected to survive 24 hours
14. Advanced chronic liver disease (Childs-Pugh Score $>$ 12) (See Appendix J)
15. Severe chronic respiratory disease with the use of home oxygen
16. Severe traumatic brain injury - defined as a patient who:
 - a. Has undergone intracranial neurosurgical intervention for monitoring or therapy (intracranial pressure monitoring, external ventricular drain, craniotomy), or

- b. Has an intracranial injury by head CT (does not include patients with minimal subarachnoid injury and/or minor skull fracture) , or
- c. Has a post-resuscitation Glasgow Coma Score (GCS) < 9 assessed after sedation interruption, or
- d. Has non-survivable head injury as assessed by neurosurgery

17. Evidence of anoxic brain injury

18. History of stroke within the last 3 years

19. No intent/unwillingness to follow lung protective ventilation strategy

20. Currently receiving extracorporeal life support (ECLS) or high-frequency oscillatory ventilation (HFOV)

21. Anticipated extubation with 24 hours of enrollment

22. Clinical evidence of left atrial hypertension as measured by a pulmonary arterial wedge pressure > 18mmHg or left ventricular failure measured by an echocardiogram with a left ventricular ejection fraction less than 40%. Clinical judgement will determine if either of these measurements need to be carried out. (If the pulmonary arterial wedge pressure declines to less than 18 mmHg, then the patient would qualify if ARDS criteria persist for at least 12 hours.)

Rationale for Exclusions

Criteria 1: Patients less than 18 years old are excluded because of limited clinical trial data with hMSCs in subjects younger than 18 years.

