8.10 Prior and Concomitant Therapy

Rescue therapies for severe ARDS, including prone ventilation, corticosteroids, inhaled vasodilators, and neuromuscular blockade will be permitted. We will record whether these therapies were administered prior to or concomitantly with hMSCs. Patients on ECLS or HFOV will be excluded from this trial. Co-enrollment in randomized clinical trials of supportive therapies such as proning will be allowed after approval from the Scientific Review Committee (includes the Principal Investigator and two other study investigators) and the Chair of the DSMB. With respect to patients with SARS-CoV-2 infection, co-enrollment in randomized clinical trials of other interventions such as pharmacologic therapies and convalescent plasma will be considered on a trial by trial basis in concert with the Scientific Review Committee and the Chair of the DSMB. The use of treatments through Emergency Use Authorization (EUA) and Expanded Access Program (EAP) studies shall not be considered an exclusion. The consideration of co-enrollment with other experimental therapy trials that target patients requiring ICU level of care must be evaluated by the Scientific Review Committee and request approval from the Chair of the DSMB. Patients who are enrolled in clinical trials targeting outpatients or patients admitted to the acute care floor with trial endpoints assessed before admission to the Intensive Care Unit will be eligible for participation.

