9.6 Concomitant Therapy

We will record the use of other pharmacologic agents that are sometimes used by clinicians in the treatment of ARDS, including glucocorticoids (dexamethasone or equivalent steroids therapy), and inhaled vasodilators or neuromuscular blockade, anticoagulant and antiplatelet treatment, immunomodulatory agents and any COVID-19 related therapies. We will also record if patients are in a prone position, receive recruitment maneuvers or extracorporeal membrane oxygenation (ECMO), or if patients are enrolled in other experimental therapy trials or treatment.

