10.4.2 Specimen Collection

1. Date and time of specimen collection
2. Time of specimen processing and storage

10.5 *Endpoint Determinations*

1. Vital status at 60 days
2. Brussels Organ dysfunction failures at days 0-14
3. SOFA score at 3 and 7 days
4. Oxygenation index ($\text{PaO}_2/\text{FiO}_2$ and mean airway pressure) at 6, 12, 18, 24, 30 and 36 hours after the initiation of study product infusion as well as on days 2, 3, and 7 if still being ventilated with positive pressure (cannot be calculated if patient is on pressure support, as the mean airway pressure is not reliable)
5. Ventilatory ratio at 6, 12, 18, 24, 30, 36 hours after the initiation of study product infusion, and on days 2, 3, 7
6. Incidence of barotrauma on days 1, 2, 3 and 7
7. Time when patient achieves pressure support ventilation with 5 cmH_2O and 5 cmH_2O positive end-expiratory pressure for 2 hours
8. Time of initiation of unassisted breathing (assuming a patient achieves 48 consecutive hours of unassisted breathing)
9. Need for re-instituting assisted or mechanical ventilation after achieving 48 consecutive hours of unassisted breathing
10. Status 48 hours after initiation of unassisted breathing
11. Need for, timing, and duration of dialysis; change in renal function as measured by creatinine
12. ICU length of stay in calendar days including ICU days after readmission to ICU
13. Hospital length of stay in calendar days
14. Discharge diagnoses and discharge disposition (home, other facility, with or without assisted ventilation)
15. WHO Ordinal Scale of Clinical Assessment at days 7, 14 and 28

10.6 *Assessments After Hospitalization*

A health status questionnaire will be conducted at 28 days, 60 days and 6 months through telephone interviews.

11 Statistical Plan

The Statistical Analysis Plan has been written along with this Protocol and provides the details of the statistical methodologies applied to this Phase 2b trial.

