Appendix D: Ventilator Management

If any of the goals a-e are not met, revert to previous ventilator settings or to PS greater than or equal to 10 cm H₂O with Positive End-expiratory Pressure and F₁O₂ = previous settings and reassess for weaning the next morning. The patient will be reassessed for weaning (Section E2) the following day.

Decision to remove ventilatory support:

If tolerance criteria for spontaneous breathing trial (a-e above) are met for at least 30 minutes, the clinical team may decide to discontinue mechanical ventilation. However, the spontaneous breathing trial can continue for up to 120 minutes if tolerance remains in question.

3. Definition of Unassisted Breathing

1. Spontaneously breathing with face mask, nasal prong oxygen, high flow nasal oxygen, or room air, OR
2. T-tube breathing, OR
3. Tracheostomy mask breathing, OR
4. CPAP ≤ 5 without PS or IMV assistance, OR
5. Use of CPAP or BIPAP solely for sleep apnea management.

4. Definition of Extubation

1. Removal of an oral or nasotracheal tube.
2. If a patient receives a tracheostomy, the time of extubation is defined as the time when the patient achieves unassisted breathing as defined in **Section 3**.

5. Completion of Ventilator Procedures

Patients will be considered to have completed the study ventilator procedures if any of the following conditions occur:

1. Death
2. Hospital discharge
3. Alive 28 days after enrollment

If a patient requires positive pressure ventilation after a period of unassisted breathing, the study ventilator procedures will resume unless the patient was discharged from the hospital or > 28 days elapsed since enrollment.

6. Removal from the Ventilator Management Protocol

Patients may be removed from the 6 ml/kg PBW tidal volume ventilation requirement if they develop neurologic conditions where hypercapnia would be contraindicated (e.g., intracranial bleeding, GCS < 8, cerebral edema, mass effect [midline shift on CT scan], papilledema, intracranial pressure monitoring, fixed pupils).

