8.4 Oxygenation Index

Oxygenation index (OI) will be used as the primary efficacy endpoint. We calculate the oxygenation index with the following validated measure of respiratory function:(5, 15)

$$OI = \frac{FiO_2 (\%) \times \text{mean airway pressure}}{PaO_2}$$

Patient must be ventilated with positive pressure to calculate OI. Otherwise, the mean airway pressure is not reliable.

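### The plan has no rule for the oxygenation index after ECMO starts, so deterioration that leads to ECMO can be understated in the primary comparison

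*SAP*

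**What the plan says.** **The OI rule.** SAP 8.4 defines OI as FiO2 (%) × mean airway pressure / PaO2 and sets one condition: "Patient must be ventilated with positive pressure to calculate OI". SAP 12.6 repeats it ("The oxygenation index will only be calculated when the patient is still being ventilated with positive pressure") and adds one exception: "If patient is on pressure support, oxygenation index will be treated as missing because the mean airway pressure is not reliable". Protocol 10.5 item 4 carries the same exception ("cannot be calculated if patient is on pressure support, as the mean airway pressure is not reliable"). None of these places mentions ECMO.

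**ECMO.** Exclusion 20 in Protocol 7.3 covers patients already on extracorporeal life support at entry. Protocol 8.10 says "Patients on ECLS or HFOV will be excluded from this trial". Protocol 9.6 has staff record whether patients "receive recruitment maneuvers or extracorporeal membrane oxygenation (ECMO), or if patients are enrolled in other experimental therapy trials". Footnote K of the time-events schedule records ECMO before randomization and on days 1 to 7. The ordinal scale (SAP 8.7, Protocol Appendix K) puts ventilation plus ECMO at 7, one step below death.

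**Who is analysed.** SAP 9 keeps every patient who starts the infusion. SAP 13.1 names death, pressure support and extubation as the reasons OI goes missing, and plans a sensitivity analysis limited to patients still on assisted ventilation at 36 hours. SAP 12.8 lists no adjustment for ECMO.

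**The concern.** OI measures how much ventilator support is needed to reach a given arterial oxygen level. Once a circuit outside the lung adds oxygen, that reading no longer holds: PaO2 partly reflects the circuit, and the ventilator settings may be reduced because of it. Both lower OI without any recovery of the lung. The plan already accepts that OI should be dropped when one component is unreliable, but applies this only to pressure support.

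At stake is the direction of bias in the single primary endpoint. Deterioration is understated in whichever arm has more ECMO. If the cells help and ECMO falls mainly on placebo, part of the benefit is hidden. If the infusion worsens gas exchange and ECMO falls mainly on the cell arm, part of the harm is masked. Ventilatory ratio (through PaCO2) and the lung injury score (through PaO2/FiO2 and PEEP) are exposed in the same way.

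**Working it through.** **1. The plan's own yardstick.** Protocol 11.1 and SAP 10 give 60 per arm, 80% power, effect size 0.43, equivalent to 1.29 OI units. The implied SD is 1.29 / 0.43 = 3.0. A single-measure comparison of two means at two-sided 5% gives 65.4% power, not 80%. With six equally correlated measures averaged (variance factor (1 + 5ρ)/6), 80% is reached at ρ of about 0.65. The documents state no correlation, so the figure is attainable but cannot be confirmed. Here 1.29 serves only as a scale.

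**2. Does OI on ECMO enter the model?**
- ECMO after infusion can occur: exclusion 20 concerns entry, and Protocol 9.6 and footnote K record ECMO afterwards.
- The patient stays in: SAP 9.
- The value is calculated if the patient is on positive pressure and not on pressure support: SAP 8.4 and 12.6. Protocol 9.5 requires assist volume control, a mode in which OI is calculated. Appendix D item 1 is looser on mode, so some ECMO patients could be on pressure support and therefore missing.
- The SAP 13.1 subgroup keeps a ventilated ECMO patient who is on an assisted mode at 36 hours.

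So, on a literal reading, circuit-supported values go into both the primary and the sensitivity analysis.

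**3. How would such a patient be scored?** The endpoint is change from pre-infusion baseline. Appendix D targets PaO2 of 55 to 80 mm Hg and directs FiO2 or PEEP down when oxygenation is above target. The documents give no on-ECMO settings, so all settings below are assumed (FiO2 % / mean airway pressure / PaO2).

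Just before ECMO: 100 × 24 / 55 = 43.6.

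On ECMO:
- 30 × 12 / 80 = 4.5
- 40 × 14 / 70 = 8.0
- 50 × 16 / 65 = 12.3
- ventilator unchanged, 100 × 24 / 80 = 30.0

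Scored change = on-ECMO OI minus baseline OI:

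| Baseline OI | Change just before ECMO | OI 4.5 | OI 8.0 | OI 12.3 | OI 30.0 |
|---|---|---|---|---|---|
| 80 × 22 / 64 = 27.5 | +16.1 | −23.0 | −19.5 | −15.2 | +2.5 |
| 70 × 18 / 70 = 18.0 | +25.6 | −13.5 | −10.0 | −5.7 | +12.0 |
| 50 × 15 / 70 = 10.7 | +32.9 | −6.2 | −2.7 | +1.6 | +19.3 |
| 40 × 12 / 80 = 6.0 | +37.6 | −1.5 | +2.0 | +6.3 | +24.0 |

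Every on-ECMO score is lower than the change just before ECMO. Only some are improvements.

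**4. Effect on an arm mean.** Let g be the amount by which on-ECMO OI understates severity, taking the pre-ECMO value as the comparison. One net extra ECMO patient in an arm of 60 shifts that arm's mean by g / 60 at the timepoints after ECMO starts.
- g = 10: 10 / 60 = 0.17, which is 13% of 1.29.
- g = 25: 25 / 60 = 0.42, which is 32% of 1.29.

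The range 10 to 25 is an assumption. The severe pre-ECMO state in step 3 gives gaps from 43.6 − 30.0 = 13.6 to 43.6 − 4.5 = 39.1 (0.23 to 0.65 units). The effect averaged over the six timepoints is smaller: ECMO starting just before 24 hours touches three of six, giving 0.17 × 3/6 = 0.08 to 0.42 × 3/6 = 0.21.

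**The case against.** **A reader might infer that an ECMO patient is always scored as a large improvement.** The documents do not support that. Change is measured from baseline, not from the value just before ECMO. With on-ECMO OI of 8.0 the score is −2.7 from a baseline of 10.7 and a worsening of +2.0 from a baseline of 6.0. With ventilator settings unchanged, all four baselines score a worsening. What stands is that the deterioration is understated.

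**The effect may be small.** No ECMO frequency is given. Moribund patients and those already on ECLS are excluded, and infusion requires two stable hours, so starts within 36 hours may be few. A balanced number across arms largely cancels. This limits any claim about size but does not supply the missing rule.

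**Protocol 8.10 might be read as removing later ECMO patients.** Read with 7.3 and 9.6 it most naturally describes entry, and SAP 9 keeps all infused patients. The wording still needs reconciling.

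**SAP 9 provides blinded review of extreme values.** Any resulting sensitivity analysis is optional, and scores such as −2.7 or +2.0 lie within one implied SD of 3.0 of no change, so they would not stand out.

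**A reader might also infer that ECMO patients gain ventilator-free days**, since Appendix D lists "Tracheostomy mask breathing, OR" under unassisted breathing. That needs such breathing while on ECMO, with survival and unassisted breathing continued to day 28. It is too speculative to pursue.

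**Conclusion.** The concern holds as a gap in the primary endpoint rule. Followed literally, the plan puts circuit-supported OI values into the primary model for an event that it foresees, records and elsewhere ranks next to death. A patient who deteriorated can be scored as improved, unchanged or less worse than in reality. The comparison is biased towards the arm with more ECMO, and the SAP 13.1 subgroup analysis does not remove this.

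The direction rests on two premises: the circuit contributes to PaO2, and ventilator settings are not raised to offset it. The size cannot be stated. The range of 0.17 to 0.42 units per net extra patient is an illustration resting on an assumed understatement of 10 to 25 units, and applies only to timepoints after ECMO starts. It is not an estimate of the bias in this trial.

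**What to change.** - **OI rule.** In SAP 8.4, 12.6 and 12.7.1 and Protocol 10.5 items 4 and 5, state that OI, ventilatory ratio and lung injury score are not calculated from gases or settings obtained after ECMO/ECLS starts, extending the pressure-support rule. Say that the whole lung injury score is withheld, because SAP 8.5 otherwise averages the components that remain.
- **Sensitivity analysis.** Setting values to missing is not enough alone: the likelihood model then treats ECMO as ignorable missingness, although it marks deterioration. Add to SAP 13.1 an analysis that assigns the patient's worst (highest) pre-ECMO OI to the remaining timepoints.
- **Data and reporting.** Record the ECMO start time, including day 0 after infusion, which footnote K does not name. Report ECMO starts within 36 hours and within 7 days by arm.
- **Consistency.** Reconcile Protocol 8.10 with 7.3 and 9.6 on whether the ECLS exclusion applies at entry only.

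The cost is a few lines of text, one extra analysis, retrieval of ECMO start times from charts and a few more missing OI values. The rule should be fixed before data lock and unblinding. It concerns scoring only and changes no decision about using ECMO.
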